#### 4. Summary and synopsis

Short title	Inflammation and infective endocarditis
Methodology	Research
Objectives / aims	
 
Define the peripheral (blood) and local (valve tissue) immune landscape in infective endocarditis (IE).
 
Confirm that cMET+ T-cells are present in patients with infective endocarditis (peripheral and local) and interrogate their functional role by flow cytometry and RNA sequencing.
 

Number of participants	100
Inclusion and exclusion criteria	
Inclusion:
 
 
The principal inclusion criteria is a clinical diagnosis of IE made according to the Duke Criteria. Patients aged 18-85 are eligible.
 
 
Exclusion:
 
 
We will exclude patients with an active solid organ or haematological malignancy as these conditions can influence immune cell frequency and phenotype.
 

Statistical methodology and analysis (if applicable)	With the support of our local NIHR bioinformatics and bio-repository facility ( http://www.whri.qmul.ac.uk/core-facilities/nihr-bioinformatics-and-bio-repository ), Multiple parameters will be analysed using multiple group comparisons (ANOVAs) to increase power.
Study duration	18 months

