## 6. Study objectives

1. We will report a comprehensive analysis of immune cell frequency and function in the peripheral blood and valve tissue from patients with IE. This has never before been performed.

2. We will confirm whether cMET+ T-cells are present in patients with IE (blood and valve), and determine if they may have a diagnostic and therapeutic potential.
3. We will compare immune phenotype during the acute disease phase in IE with convalescence/recovery.

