### Sample size and power calculations

The total sample size for this project is 100 patients with IE. We will aim to recruit to 5 IE subgroups (n=20 per subgroup), to reflect the heterogeneous nature of this condition: native valve, prosthetic valve, cardiac-device related, uncorrected GUCH and recurrent IE. Power calculations were performed using G\*Power (University of Kiel, Germany) with the support of the QMUL Bioinformatics department. Sample size estimates were based on a Wilcoxon-Mann-Whitney test using the following parameters:  $\alpha = 0.05$ ,  $\beta = 0.2$ , predicted effect size 0.87. The predicted effect size used for this power calculation was based on a previously published study comparing the % of peripheral cMET+ T-cells in acute myocarditis and DCM6. Using the above calculation, we determined that a minimum sample size of 10 patients per subgroup would yield statistical significance. To avoid under-powering, we chose to double this target to 20 patients per subgroup.

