### Method of analysis

- 1) Flow cytometry of immune cell. Whole blood flow cytometry is a well-established method. [name] laboratory has access to a flow cytometry core facility, which has machines that can identify up to 12 phenotypic markers on any given cell. Moreover, we, have extensive experience in immune cell phenotyping using this method. The key advantages are:
  - It is the gold-standard for immune cell phenotyping
  - A minimal amount of blood is needed (max 200 $\mu$ l; 50 $\mu$ l per patient per antibody panel -see table 3 below)
  - Antibodies are commercially available and have been extensively validated by ourselves and others.

All samples will be processed and analysed within 1 hour of sample collection to minimise degradation of proteins on the surface of the immune cells.

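### The synopsis justifies multi-parameter ANOVAs as a way to increase power, but analysing more parameters raises the power of no comparison and creates a multiplicity problem instead

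*Protocol*

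**What the plan says.** The only statement in the protocol on how groups will be compared is in section 4, under statistical methodology: "Multiple parameters will be analysed using multiple group comparisons (ANOVAs) to increase power". Section 10, under Method of analysis, describes flow cytometry and no statistical method.

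The sample size in section 10 has a different basis: "Sample size estimates were based on a Wilcoxon-Mann-Whitney test using the following parameters", with alpha 0.05, beta 0.2 and "predicted effect size 0.87". The effect size comes from one variable, the percentage of peripheral cMET+ T-cells. The groups are set out there too: "We will aim to recruit to 5 IE subgroups (n=20 per subgroup", 100 patients in all.

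The number of parameters is not stated. The scope is broad: section 6 promises a "comprehensive analysis of immune cell frequency and function in the peripheral blood and valve tissue". Section 10 mentions a core facility "which has machines that can identify up to 12 phenotypic markers on any given cell", and at most 200 µl of blood at 50 µl "per patient per antibody panel". Section 15 adds plasma factors and spatial RNA sequencing of valve tissue.

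**The concern.** The power of a test depends on its effect size, sample size, variance and alpha. The number of other variables tested in the same patients does not enter. If each extra parameter is tested at an unchanged alpha, the chance of at least one false positive grows. If alpha is divided among them, each test loses power. The synopsis therefore presents as a strength something that needs to be controlled.

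What is at stake is the reading of subgroup differences. Section 5 links cMET+ T-cell frequency to possible diagnostic use and targeted immunological therapy. A chance difference between types of endocarditis, found among many readouts, could steer that work. The variable on which the study was sized is not set apart from the rest for the subgroup comparison.

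**Working it through.** **Inputs.** From protocol section 10: five subgroups, 20 per group, effect size 0.87, alpha 0.05 (given for the sample size only), up to 12 markers per cell, at most 200 µl at 50 µl per panel. Assumptions made here: 0.87 is a standardised mean difference d (the metric is not named); each ANOVA is tested at 0.05; readouts are normal; no true differences where false positives are counted.

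**The plan's own figure.** The protocol says "a minimum sample size of 10 patients per subgroup would yield statistical significance". With d = 0.87, alpha 0.05 two-sided and 80% power, the normal approximation gives n = 2 × (1.96 + 0.84)² / 0.87² = 20.7, so 21 per group; the t test needs 22 and the Wilcoxon test 23. One-sided, the figures are 17, 18 and 18. Ten is not reproduced. That is a separate matter; only d = 0.87 and n = 20 are carried forward.

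**Does ANOVA over five groups add power?** For one pair, the noncentrality is 0.87 × √(20/2) = 2.75 either way. Pooling the variance over five groups raises the degrees of freedom from 38 to 95. Power rises from 76.5% to 77.7%. This small gain comes from having several groups, not several parameters.

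**What do more parameters do if alpha is corrected?** Take one group shifted by d = 0.87. Then f = 0.87 × √(0.2 × 0.8) = 0.348 and the noncentrality is 100 × 0.348² = 12.1. Power of the omnibus F test (4 and 95 degrees of freedom) under Bonferroni:

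| Parameters | Alpha per test | Power |
|---|---|---|
| 1 | 0.05 | 78% |
| 12 | 0.0042 | 44% |
| 48 | 0.0010 | 28% |

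The 78% depends on the pattern of means; other patterns with the same largest difference give 55% to 93%.

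**What do they do if alpha is not corrected?** The expected number of false positives is 0.05 × m, and the chance of at least one among independent tests is 1 − 0.95^m. Twelve is the stated marker capacity. Forty-eight is an illustration: 200/50 = 4 panels, times 12. Values under correlation are from simulations of five groups of 20; ranges show the spread between runs.

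| Readouts | Expected | Independent | Correlation 0.5 | Correlation 0.8 |
|---|---|---|---|---|
| 12 | 0.6 | 46% | 32–34% | 19–20% |
| 48 | 2.4 | 91% | 61–64% | 31–33% |

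Correlation leaves the expected number unchanged but makes it more skewed. With 48 readouts the median number of false positives is 2 if independent, 1 at correlation 0.5 and 0 at 0.8.

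**Within one parameter.** Five groups form 5 × 4 / 2 = 10 pairs. Ten unadjusted pairwise tests at 0.05 give about a 28% chance of at least one false positive (simulation).

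**The case against.** The best defence is that the power phrase attaches to the ANOVAs and not to the parameters. One omnibus test does replace ten pairwise tests for each parameter, and it does pool the variance. That much stands, so it would be too strong to say the plan does nothing but multiply tests. The gain is about one percentage point, however, and it does not support the claim made for multiple parameters.

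A reader might infer that several false-positive immune differences are to be expected. The documents do not support that. They give no parameter count, and 0.05 appears only as a sample-size input. The figure of 12 is what the machines can identify, and 48 is built from that capacity and a maximum blood volume. A marker is also not the same as a readout: some markers only define a population. With 12 readouts the expectation is 0.6, below one.

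A reader might also infer that no multiplicity control exists. Only the protocol was available, and such a rule may sit in a statistical analysis plan, so its absence from the protocol is not the point made here. The point is a stated rationale that no analysis plan could make correct.

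The objectives are mostly descriptive, and the percentage of cMET+ T-cells is already prominent in the aims and the sample size. Both are true, and both lower the severity.

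**Conclusion.** The statement is wrong as written. Analysing more parameters raises the power of no comparison, and the five-group ANOVA adds only the pooling gain of about one point. The cost runs the other way: a false-positive chance above the nominal 5%, or lower power per test once alpha is shared. Even 12 readouts correlated at 0.8 give roughly 20%, about four times nominal.

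These sizes rest on an assumed alpha of 0.05 per ANOVA, on no true differences, and on readout counts that the protocol does not fix. They show the direction and plausible range; they do not predict this study's results. The power figures also assume that 0.87 is a standardised mean difference. Because the study is largely descriptive and the detailed procedure can be placed in the analysis plan, this should be fixed but is not a must-fix.

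**What to change.** In section 4, delete the closing words that claim a gain in power. In section 10, name the percentage of cMET+ T-cells in recruitment blood, which the sample size already uses, as the lead variable for the subgroup comparison. Give it one global test across the five subgroups at 0.05, followed by multiplicity-adjusted pairwise contrasts. Label all other flow cytometry, plasma and RNA readouts exploratory, under false discovery rate control, with the exact procedure left to the statistical analysis plan. This governs the subgroup comparison only; the objectives on presence of the cells and on acute versus convalescent phase stay as they are.

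The cost is a few sentences and no extra patients or assays. Fewer secondary readouts will be nominally significant, and pairwise contrasts lose power: for d = 0.87 and 20 per group, a two-sided Wilcoxon comparison falls from about 74% at 0.05 to about 40% at 0.005, the strictest step when ten pairs are adjusted.

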## 5. Introduction

### Background

Infective endocarditis (IE) is challenging to diagnose and manage. Its frequency is increasing as we perform more interventions on patients with pre-existing valve disease. Current strategies are relatively historical; patients require positive blood cultures for a definitive diagnosis and are typically managed with intravenous antibiotics and cardiac surgery. While the immunological complications of IE are well recognised (e.g. glomerulonephritis, rheumatoid factor positivity), there has been very little research to explore the immune system's role in disease onset and progression. Our laboratory has discovered and characterised a group of circulating immune cells (cMET+ T-cells) that appear to have a direct role in the progression of another inflammatory heart disease known as myocarditis. Pilot data (also from our laboratory, n=3 patients) suggests that these cells are detectable in explanted valve tissue from patients undergoing endocarditis surgery. We believe that the presence of these cells in IE implies that there may be a significant contribution to disease progression from the immune system. It is possible that the exposure of cardiac proteins by damage caused by a bacterial infection primes the immune system against self, and that these auto-reactive T-cells then go on to attack and destroy native valve tissue.

### Rationale

We would like to investigate whether circulating and valvular cMET+ T-cells are detectable across the wide spectrum of patients with IE and further explore their role in this condition. We are planning to functionally characterise both circulating immune cells and those that are detectable in explanted valve tissue using a combination of flow cytometry and spatial RNA sequencing. We hypothesise that cMET+ T-cells may have utility in the diagnosis of IE and that in patients with a significantly elevated frequency of cMET+ T-cells, we might be able to offer novel (and highly specific) targeted immunological therapy that could improve patient outcomes. To address this hypothesis, we will undertake an observational cohort study in patients with IE to analyse the immune cell status in the peripheral blood and valve tissue (obtained at surgical explant)

### Risks / benefits

We do not envisage any risks to this project as we will only be taking blood samples via venepuncture. Only a slight discomfort may be experienced by the patient at the injection site and slight bruising. To minimise bruising, the patient will be advised to apply pressure to the venepuncture site using a cotton swab that will be provided to the patient once the blood has been taken. The patient will also be advised to sit for 10 minutes to ensure that they are feeling well after the blood is taken.

The potential benefit of this project outweighs the potential risks. The immediate outcomes for this project is to gain a detailed understanding of how the immune system could affect the development and progression of infective endocarditis. This could help to inform our current understanding of why infective endocarditis occurs and help us to develop new treatments.

## 6. Study objectives

1. We will report a comprehensive analysis of immune cell frequency and function in the peripheral blood and valve tissue from patients with IE. This has never before been performed.

2. We will confirm whether cMET+ T-cells are present in patients with IE (blood and valve), and determine if they may have a diagnostic and therapeutic potential.
3. We will compare immune phenotype during the acute disease phase in IE with convalescence/recovery.

## 7. Study population

All patients with IE who are managed within the Barts Heart Centre.

### Inclusion criteria

- The principal inclusion criteria is a clinical diagnosis of IE made according to the Duke Criteria.
- Patients aged 18-85 are eligible.
- Fluency in English (otherwise interpreters will be used)
- Informed, written consent

### Exclusion criteria

- Unwilling or unable to give consent
- Participants who are unable to understand written English
- Patients with an active solid organ or haematological malignancy

## 9. Study procedures

- Laboratory assessments (Please see the laboratories section 12)

- Participant withdrawal (including data collection, retention or replacement for withdrawn participants):

Participants will have the option to submit a written request to be withdrawn from the study at any stage. Participants will also have the option to withdraw consent from further participation in which circumstance no further data will be collected for inclusion. In the unfortunate event that a participant loses capacity, information gathered will continue to be used but no further data will be recorded. The end of the study will be defined by achieving the proposed patient numbers per patient group (outlined above).

## 10. Statistical considerations

The CI declares responsibility for the statistics and statistical oversight of the study (see CI Signature Agreement section 3).

### Sample size and power calculations

The total sample size for this project is 100 patients with IE. We will aim to recruit to 5 IE subgroups (n=20 per subgroup), to reflect the heterogeneous nature of this condition: native valve, prosthetic valve, cardiac-device related, uncorrected GUCH and recurrent IE. Power calculations were performed using G\*Power (University of Kiel, Germany) with the support of the QMUL Bioinformatics department. Sample size estimates were based on a Wilcoxon-Mann-Whitney test using the following parameters:  $\alpha = 0.05$ ,  $\beta = 0.2$ , predicted effect size 0.87. The predicted effect size used for this power calculation was based on a previously published study comparing the % of peripheral cMET+ T-cells in acute myocarditis and DCM6. Using the above calculation, we determined that a minimum sample size of 10 patients per subgroup would yield statistical significance. To avoid under-powering, we chose to double this target to 20 patients per subgroup.

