## 11. Ethics

Application for the current study is pending following submission (IRAS ID 353031).

Informed consent will be obtained and recorded as described as above. Allowances for special groups are detailed above.

The CI will ensure that this study is conducted in full conformity with the current revision of the Declaration of Helsinki (last amended October 2013) on research involving human subjects.

The CI will ensure that the study is conducted in accordance with all applicable regulatory requirements which are based on ICH Guidelines for GCP, Trust and Research Office policies and procedures and any subsequent amendments.

The study can only start after approval from a REC, HRA and confirmation of local capacity and capability at each of the participating centres.

Members of the study team do not have any conflicts of interest to declare.

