## 19. Finance and funding

This study is in the process of peer review and a funding application has been made to the Barts Charity (ID 27360).

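### If the effect size of 0.87 is a standardised difference d, the stated minimum of 10 per subgroup is not reproduced for the usual parent distributions; metric, sidedness and parent are not stated

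*Protocol*

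**What the plan says.** Protocol section 10, under the sample size heading, plans 100 patients in five subgroups of 20. The basis is a two-group rank test: "Sample size estimates were based on a Wilcoxon-Mann-Whitney test using the following parameters", followed by alpha 0.05, beta 0.2 and "predicted effect size 0.87". The effect size is taken from a published comparison of the percentage of peripheral cMET+ T-cells in acute myocarditis and DCM; no means, SDs or group data are given. The result is "we determined that a minimum sample size of 10 patients per subgroup would yield statistical significance", and then "To avoid under-powering, we chose to double this target to 20 patients per subgroup".

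Neither this paragraph nor any other part of the protocol gives the metric of 0.87, the number of sides or the parent distribution. Section 9 ties the end of the study to these numbers: "The end of the study will be defined by achieving the proposed patient numbers per patient group".

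**The concern.** A reader will most readily take an effect size of 0.87 beside a two-group test as a standardised mean difference d. On that reading 10 per group looks far too small for 80% power. If the base figure does not hold, neither does the claim that 20 is a doubling that protects against low power.

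This paragraph is the only quantitative basis for the 100-patient design. Depending on what 0.87 means, 20 per subgroup either carries a real twofold margin or, for a two-sided test with normal data, is about 3 per group short of the protocol's own 80% target. The text does not let a reader tell which.

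**Working it through.** **Inputs from the protocol (section 10).** Alpha 0.05; power 1 − 0.2 = 0.80; effect size 0.87; Wilcoxon-Mann-Whitney test; equal subgroups; stated minimum 10; planned 20.

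**Assumptions, because the protocol is silent.** Metric: d or P(X>Y). Sides: one or two. Parent: several, as listed.

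**1. A reading that returns the plan's figure: 0.87 as P(X>Y).** Noether's formula for equal groups is

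n per group = (z for 1 − α/2 + z for power)² / [6 (P − 0.5)²]

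Two-sided: (1.960 + 0.842)² / (6 × 0.37²) = 7.849 / 0.8214 = 9.56, so 10. One-sided it gives 7.53, so 8. By the same formula, two-sided power is 82% at 10 and 98% at 20. Exact simulation with normal data (P = 0.87 corresponds to d = 1.593) reaches 82% at 8, 89% at 10 and over 99% at 20.

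**2. 0.87 as d, efficiency method.** Replace n by k = n × ARE in the two-sample noncentral t, with df = 2k − 2 and noncentrality d√(k/2). The ARE is 3/π for a normal parent, π²/9 for logistic, 1.5 for Laplace and 0.864 for the minimum.

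Normal parent, two-sided:
- n = 10: k = 9.55, df = 17.1, noncentrality 0.87 × √4.775 = 1.90, power 43%.
- n = 20: k = 19.10, df = 36.2, noncentrality 2.69, power 74%.
- n = 22 gives 78.6% and n = 23 gives 80.4%, so 23 are needed.

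Per-group need for 80% power:

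| Parent | Two-sided | One-sided |
|---|---|---|
| Normal | 23 | 18 |
| Logistic | 20 | 16 |
| Laplace | 15 | 12 |
| Minimum efficiency | 26 | 20 |

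**3. 0.87 as d, simulation of the exact test** (location shift of 0.87 SD). The efficiency method is too favourable for Laplace data at these sizes (two-sided power at 10 is 63% by that method, 52% exact), so the exact values should be preferred.

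| Parent | Need, two-sided | Need, one-sided | Two-sided power at 10 | Two-sided power at 20 |
|---|---|---|---|---|
| Normal | 23 | 19 | 41% | 74% |
| Logistic | 21 | 17 | 45% | 79% |
| Laplace | 18 | 14 | 52% | 85% |

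Exact one-sided power at 10 is about 55%, 59% and 65%; at 20 it is about 83%, 87% and 92%.

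**4. 0.87 as d, skewed parent, exact simulation at n = 10.** Strong skew recovers the figure: lognormal with sigma 0.9 gives about 80% two-sided, sigma 1 gives 84% two-sided (99% at 20), and sigma 0.75 gives 82% one-sided. Milder skew does not: exponential gives 62% and lognormal with sigma 0.5 gives 56%, both two-sided.

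**5. What 20 per group supports.** For a normal parent, two-sided, 80% power at 20 per group requires d of about 0.94 (exact simulation).

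**The case against.** The strongest reply is that no error has been shown. The protocol never calls 0.87 a d. Read as P(X>Y), a standard formula returns exactly 10. Even as d, a percentage of cells could well be skewed, and the choice of a rank test fits that; with a strongly skewed lognormal parent 10 per group is enough. The cited study is not at hand, so the metric cannot be settled here. The study also recruits 20, not 10, in an observational cohort with largely descriptive aims, so nothing in its conduct changes.

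Most of this stands, and it limits the point. A reader might infer that the sample size is wrong or the study underpowered. The documents do not support that, because both conclusions need a metric and a parent that the protocol does not give.

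What does not stand is the suggestion that this is mere missing detail. The protocol prints a finished calculation and a margin of safety, and the inputs printed beside them are compatible with needs from about 8 to 26 per group.

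Two related remarks are side points. A sample size gives power and does not produce significance, but beta is stated, so that is a matter of wording. The synopsis plans "Multiple parameters will be analysed using multiple group comparisons (ANOVAs) to increase power"; this bears on how far a two-group power figure reaches, not on whether 10 is reproduced.

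**Conclusion.** The point holds conditionally. If 0.87 is d, the minimum of 10 is not reproduced for a normal, logistic, Laplace or minimum-efficiency parent, one- or two-sided, and 20 is not twice the need. Under a two-sided test, 20 per subgroup falls short of the stated 80% for normal data (74%) and marginally for logistic data (79%), but exceeds it for Laplace data (85%). One-sided, 20 reaches 80% for all three, though still without a twofold margin.

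If 0.87 is P(X>Y), or is d with a strongly skewed parent, 10 is about right and the doubling is real. The protocol does not say which applies, so the established defect is a sample-size figure that cannot be verified and that fails under the most natural reading. It should be fixed; confidence is medium because the metric is unknown.

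**What to change.** Keep 20 per subgroup. Rerun the calculation and state the metric of 0.87, the number of sides and the parent distribution.

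- **Unless the rerun returns 10**, delete the minimum of 10 and the doubling claim, and write, for example: *With 20 per subgroup, one unadjusted pairwise two-sided 5% Wilcoxon-Mann-Whitney comparison (normal parent) has about 74% power for d = 0.87, and 80% power for d of about 0.94.* The words on a single unadjusted pair matter, because the synopsis plans comparisons across several groups.
- **If 0.87 is P(X>Y), or a skewed parent was used**, say so and give the power at 10 and at 20 by that one method.
- **In either case**, word the result as power rather than as significance.

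The cost is one paragraph, with no extra patients and no design change. The downside is a slightly less favourable stated power if 0.87 is d with a two-sided test and a normal parent. The protocol describes approval and funding as still open (section 11: "Application for the current study is pending following submission"; section 19: "This study is in the process of peer review and a funding application has been made"), so on its own account the paragraph can be corrected before those decisions rest on it.
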